### Figure 3 The construct of OBP-301

Specificity to cancer is derived by exploiting differential (normal versus tumor) cell surface or intracellular aberrations in gene expression that arise in malignancies. Telomerase activation is considered to be a critical step in carcinogenesis, and its activity is closely correlated with hTERT expression. Thus, expression of hTERT is generally low in differentiated adult cells, and active in cells with proliferative capacity such as tumors, gastrointestinal endothelium, or stem cells  with the majority of malignant tumors shown to demonstrate high telomerase activity. Previous studies have demonstrated control over the expression of exogenous genes to telomerase-positive cancer cells by the hTERT promoter  and the hTERT promoter is an excellent candidate for generating cancer-specific oncolytic adenovirus.

There are several mechanisms by which adenoviruses in general, and OBP-301 in particular, can destroy tumor cells *in vivo*. Direct cell lysis occurs following viral replication and data from animal models have shown that non-replicating adenovirus in rodent tissue will induce both an acute (2-4 days) and chronic (14 days) inflammatory infiltration. During the acute phase, tumor necrosis factor (TNF- $\alpha$ ) and interleukin (IL)-1 and IL-6 are produced in high concentrations locally within the tissue. These cytokines have both direct cytopathic effects and indirect effects through immune effector cell recruitment into the local tissue. Finally, adenovirus infection of a tumor cell may augment tumor antigen presentation and enhance tumor antigenicity, leading in turn to improved recognition and destruction of tumors by cytotoxic T cells.

*In vitro* studies have validated the selective infectivity and direct cytolysis of OBP-301 in cancer cells and *in vivo*, intratumoral injection has demonstrated anti-tumor activity without significant

#### Page 22 V8.0

toxicity. Additionally, distant viral uptake was observed following intratumoral injection, evidenced by the presence of adenoviral protein in non-injected tumors following treatment of the contralateral tumor. These encouraging pre-clinical findings of safety and directed anti-tumor activity were supportive of the continuing clinical development of OBP-301 as an oncolytic therapeutic agent.

Summary of Non-Clinical and Clinical Studies

# 1.1.1 Non-Clinical Studies

The pre-clinical experience with OBP-301 is described in further detail in the Investigator's Brochure . Non-clinical studies have investigated OBP-301 mechanism of action and clinical proof-of-concept in a) cytotoxicity studies using normal and tumor cells, and b) tumor-bearing xenograft mouse models. The safety of OBP-301 has been characterized in animal models that exhibit tumors (xenograft models) as well as in non-tumor models (normal cotton rats, *Sigmodon hispidus*). The primary safety studies for OBP-301 were conducted in cotton rats, a species selected based on information available in the literature, which suggested that this was a relevant and semi- permissive model for adenoviral safety characterization and reflecting a pre-investigational new drug application (pre-IND) discussion with the Center for Biologics Evaluation and Research (CBER) at the US Food and Drug Administration (FDA).

Due to issues with the generation of homologous recombinants when using an human embryonic kidney cell (HEK)293 cell substrate for OBP-301 manufacture, transfer to a HeLa cell-based production system was implemented after pre-clinical studies had been initiated. The HEK293 cell-based material may have contained wild-type Ad5, which may have contributed to the observed oncolytic activity. Comparability studies undertaken in the rodent toxicology species, consisting of extended product characterization and a comparison of the toxicological effect of the HEK293 and HeLa OBP-301 material, have demonstrated equivalence between OBP-301 virus produced through either production system.

# 1.1.1.1 Non-clinical Pharmacology

*In vitro* studies have demonstrated cytopathic activity of OBP-301 on a variety of human tumor cell lines derived from different organs relevant to the clinical setting, as evaluated by a cell viability assay (XTT assay). OBP-301 oncolytic activity in tumor cells was found to be similar compared to another engineered oncolytic virus, and was similar to or slightly weaker than that of wild-type Ad-5 depending on the target tumor cell type. Cytopathic activity of OBP-301 in human normal cell lines was also evaluated, using a variety of methods (XTT assay, plaque assay, Coomassie Blue staining), including assays for E1A mRNA and protein expression, which served as surrogates for viral replication. A correlation between the expression of E1A, hTERT activity and viral replication at the early stage of infection appeared to be present. In normal cells, OBP-301 is less cytotoxic than wild-type Ad5, while in tumor cell lines, OBP-301 showed cytopathic effects equivalent to wild-type Ad5. This is indicative of selective replication in the tumor cells.

In mechanism-of-action studies, there appeared to be a correlation between E1A expression (assessed by immunoblot) and hTERT mRNA expression levels in tumor cells at the early stage of infection. In addition, a correlation between Coxsackie adenovirus receptor (CAR) expression and cytopathic effect of OBP-301 was noted for tumor cells. *In vivo*, the human tumor-bearing xenograft mouse model was utilized in order to define a potentially efficacious dose and regimen.

In the first study, multiple intratumoral injections of OBP-301 E3 (-) and E3 (+) both resulted in equivalent inhibition of tumor growth. A second study demonstrated OBP-301 replication in non-injected distant tumors, as evaluated by RT-PCR for E1A mRNA and immunohistochemistry using an anti-E1A antibody, indicating the potential for OBP-301 to reach and then replicate in distally located tumors. The dose of  $3.6 \times 10^9$  viral particles (VP)/animal intratumoral injection in the xenograft model achieved the anticipated anti-tumor effect, and no drug-related death has been observed.

### 1.1.1.2 Toxicology

In total, 4 single dosing toxicological studies with OBP-301, including 2 single non-Good Laboratory Practice (GLP) study and 2 GLP studies, have been undertaken. Most of the data gathered from non-GLP and GLP studies assessed the route in animals most similar to human intratumoral dosing, being the intramuscular (IM) route. Toxicity evaluation following IM injection of OBP-301 in rats did not show a formal no effect level (NOEL). However, the low dose group, 10^9 VP/animal (approximately 10^10 VP/kg) showed only sporadic, minimal-to-mild, transient microscopic changes in the liver on Day 28, and these changes were no longer apparent by day 85 after treatment. Therefore, this dose was designated to be the No Adverse Effect Level (NOAEL). A higher IM dose, 10^11 VP/kg (dose group 3 in FXT00014) as well as the highest dose, showed minimal-to-mild sporadic hepatocellular damage on histopathological evaluation. No animals experienced morbid changes, weight loss, or deaths when 10^11 VP/animal (approximately 10^12 VP/kg) was administered via either the intravenous (IV) or IM route.

In the pilot repeated dose study, rats (15 males and 15 females) were assigned into 3 groups, Group 1: Control group, Group 2: 7 days repeated dosing and Group 3: 14 days repeated dosing. Both groups 2 and 3 had a 7-day Follow-Up Period following the dosing phase. The results of this study demonstrated that repeat dosing of IM administered OBP-301 to cotton rats at  $1 \times 10^{11}$  VP/animal for 7 or 14 day was well tolerated. No significant differences were observed in animals dosed for either 7 or 14 days.

In the single dose toxicity study of intra-hepatic injection, histopathologic findings were observed including adhesion, fibrinous inflammation, granulomatous inflammation, and necrosis in the liver on Day 5 and adhesion and fibrosis in the liver on Day 14 in both genders at  $1 \times 10^{11}$  VP/kg. However, no mortality, or observations of clinical signs, body weight and food consumption changes were reported. Systemic distribution of virus away from the injection site was noted in these studies with quantitative PCR (qPCR) data at 10^11 VP/animal indicating the presence of viral DNA in the liver (and to a lesser extent in the lung) out to and including Day 85. These data showed continued presence of viral DNA in normal liver, which may signify that the toxicity on histopathologic evaluation in the liver was test article related (highest dose only, other dose groups were not evaluated for persistence). However, the continued presence of viral DNA in the highest dose group did not result in accrual of toxicity with lesions identified on Day 85, particularly the liver lesions noted above, no more severe than those observed at earlier time points. In addition, the pattern of persistence was consistent with results from other replication-competent oncolytic adenoviruses (see December 2005 RAC Meeting Documents Tab 2397, Protocol Number 0510-732: A Phase I/II Dose Escalation Trial of Intratumoral Injection with Oncolytic Adenoviral Vector INGN 007 (VRX-007) in Patients with Advanced Solid Tumours). IM compared to IV administration was shown to limit toxicity, and all toxicities were reflected in the biomarker surrogates of clinical pathology.

Dosing in human patients will utilize a conservative dose extrapolation paradigm and offers an adequate safety margin for systemic toxicity. The human equivalent dose (HED) is calculated on a body weight-adjusted basis (to  $10^{10}$  VP/kg × 70 kg, or 7 ×  $10^{11}$  VP; the HED). The highest proposed clinical dose of  $1 \times 10^{12}$  VP (equivalent to ~ $1.4 \times 10^{10}$  VP/kg) is equivalent to the NOAEL dose in the animal studies.

#### 1.1.2 Clinical Studies

Clinical trials of OBP-301 administered by intratumoral injection have been conducted in patients with advanced cancer under the following protocols:

#### **Completed** studies

• OBP-301-001: an open-label, dose-escalation study. The first human study evaluating sequential doses of a single  $(1 \times 10^{10} \text{ to } 1 \times 10^{12} \text{ VP/tumor})$  and repeated  $(1 \times 10^{12} \text{ VP/tumor})$  intratumoral injection of OBP-301 in patients with advanced solid carcinoma. The first patient was enrolled on 30 October 2006 and the last patient completed follow-up on 24 October 2011. Twenty-two patients (n = 13 female, n = 9 male) were treated and analysed. Patients with the following tumor types participated in the Phase 1 trial: 5 patients with melanoma, 4 with squamous cell carcinoma of the head and neck, 3 with breast cancer, 2 with soft-tissue sarcoma, and 1 each with squamous cell carcinoma primary unknown, carcinoma of the salivary gland, non-small cell lung cancer, neuroendocrine tumor, basal cell carcinoma, carcinoma of the gall bladder, pancreatic carcinoma, and cancer of the vulva. Of these, 3 patients (1 patient with carcinoma of the breast and the 2 patients with carcinoma of OBP-301, all into the liver. The study was conducted under the current IND for OBP-301.

OBP-301 was found to be well tolerated in this Phase I study. No dose-limiting toxicities (DLTs) were experienced by any of the 22 patients treated with OBP-301 in this study; therefore, the maximum tolerated dose (MTD) could not be determined. Analysis of all safety data from this study demonstrated an acceptable safety profile with intratumoral injection of OBP-301 with types of events reported that were similar to those reported in patients receiving other adenovirus vectors. Signals of efficacy were seen even in patients treated with a single intratumoral injection. Most patients had stable disease after treatment (15/17); 2 patients reported progressive disease on Day 28. One additional patient who had stable disease on Day 28 reported progressive disease on Day 56. In patients followed for up to 5 years after study participation, there was no signal of a safety concern related to OBP-301 treatment.

### **Ongoing studies**

- CT-OT-21 (OBP-301-002-B-H): a Phase I/II Study to Evaluate the Safety and Efficacy of OBP-301 at doses of  $1 \times 10^{10}$  VP/tumor and  $1 \times 10^{12}$  VP/tumor in patients with hepatocellular carcinoma. The study aims to recruit a maximum of 36 patients from 2 clinical trial sites in two countries, Taiwan and Korea. A maximum of 36 patients with hepatocellular carcinoma meeting all inclusion criteria and none of the exclusion criteria will be recruited in the trial. For dosing cohorts of at least 3 patients each are planned to be sequentially accrued until study agent related DLT is met in equal or more than 2 patients at whichever dose level. Recruitment to this study commenced in November 2014.
- In this study, the safety of more than 2 mL has been investigated. In single dose cohorts, 3mL of 1x1012 VP/mL (3x1012 VP) was administered in 3 subjects and no DLT was observed.
- OBP-301-003-C-V: a Phase I/II dose-escalation study to determine the safety and efficacy of OBP-301 at doses of 1 × 10^10 VP/tumor and 1 × 10^12 VP/tumor in patients with head and neck, esophagus and lung cancers with radiation therapy is being conducted in Japan under Ministry of Health, Labour and Welfare (MHLW) approval (granted on 13 July 2012). The study was initiated on 29 November 2013 and aims to recruit a maximum of 24 patients from Okayama University Hospital in Japan. The primary objectives are assess the clinical safety of OBP-301 in combination with radiotherapy in patients with head and neck, esophagus, and lung cancers; to determine the MTD/maximum feasible dose (MFD) of OBP-301 and to assess the DLT of OBP-301. Secondary objectives for this study include determination of the tumor response rate of OBP-301 and the duration of response and overall survival.
  - In OBP-301-003-CV (OBP-301 + Radiation phase I study, NCT0321305), the safety was monitored when OBP-301 were administered in the dosing levels of; 1 mL of 1x10^10 VP/mL(Level 1), I mL of 1x10^11 VP/mL(Level 2), and 1mL of 1x10^12 VP/mL (Level 3), 3 times of the administration, with the dose escalation study design. The dose difference between the level was 10 times and 100 times of OBP-301 compared to Level 1 was tested in the Level 3, resulted in no DLT and no any intolerable adverse events.

- Thus far, no dose limiting toxicities have been observed. Specifically in esophageal cancer, 13 patients have been enrolled and have received OBP-301 with radiaiton, with no dose limiting adverse events.
- TL03001: a Phase IIa Study to Evaluate the Efficacy, Safety, and Immunological Response of OBP-301, Telomerase Specific Replication-competent Oncolytic Adenovirus in Patients with Unresectable Metastatic Melanoma. This study aims to recruit a maximum of 50 patients in the US. Recruitment to this study commenced in July 2017.
- TL04001: a phase 1 study to evaluate the safety of OBP-301, OBP-301 in combination with radiation therapy in patients with esophageal cancer not applicable for standard therapy. The study aims to recruit a maximum of 12 patients in two sites in Japan. Recruitment to this study commenced in July 2017.
  - In addition, in TL04001, the cohort 2 (1mL of 1x1012 VP/mL, 3 times biweekly) is ongoing and no DLT was observed so far.
- EPOC1505: a phase I study to evaluate the safety and potential efficacy of OBP-301 in combination with Pembrolizumab in patients with advanced or metastatic solid tumors. This study aims to recruit a maximum of 28 patients in two sites in Japan. Recruitment to this study commenced in December 2017.

### 1.2 Summary of Potential Risks and Benefits

The side effects listed below are expected based on those seen with the same type of adenovirusbased oncolytic agents in human trials and are anticipated from non-clinical toxicological studies of OBP-301 treatment:

Transient fever	Chills
Injection site pain	Injection site inflammation
Flu-like symptoms	Fatigue
Nausea	Vomiting
Headache	Lymphopenia
Myalgia	Neutropenia
Pneumonia	Leukopenia
Transaminitis	

In the Phase I study conducted in patients with advanced cancers (OBP-301-001), intratumoral injection with OBP-301 at dose of  $1 \times 10^{10}$  VP/tumor and  $1 \times 10^{12}$  VP/tumor was well tolerated with no DLTs reported . Five patients reported 9 serious adverse events (SAEs) of dysphagia and difficulty breathing, syncope, intractable pain, ECG T-wave abnormality, abdominal pain, ascites, hypotension, chills and pyrexia. Although only patients in the 2 highest dose cohorts reported SAEs, none of the events occurred in more than one patient. SAEs of chills and pyrexia were considered related to drug treatment whereas the causality of all other SAEs was assigned to tumor progression, prior medical conditions, and/or dehydration. Decreases in lymphocytes were noted at the time of treatment, but these changes were transient and returned to baseline levels by no later than Day 7. The changes were not considered to reflect drug toxicity. No consistent changes were observed in the hematological or biochemical laboratory parameters and there was

no indication of hepatic, renal or bone marrow toxicity. In summary, analysis of available safety data from this Phase I study demonstrated an acceptable safety profile for intratumoral injection of OBP-301, which exhibited similar events to those reported in patients receiving comparable adenovirus vectors.

There are no known direct benefits to the participants in this study.

### **1.3 Dosage and Treatment Periods**

The OBP-301 NOAEL in a GLP rodent species toxicology study was  $10^9$  VP/animal (approximately  $10^{10}$  VP/kg). Higher doses (> $10^{11}$  VP/kg), administered IM, showed minimal-tomild sporadic hepatocellular damage on histopathological evaluation but no animals experienced morbid changes, weight loss, or deaths when  $10^{11}$  VP/animal (approximately  $10^{12}$ VP/kg) was administered either via the intravenous (IV) or IM route. Furthermore, administration of  $3.6 \times 10^9$ VP via intratumoral injection in a pre-clinical xenograft model achieved demonstrated oncolytic activity. The HED is calculated on a body weight-adjusted basis (to  $10^{10}$  VP/kg × 70 kg, or  $7 \times 10^{11}$  VP; the HED) with the highest proposed clinical dose in this study,  $1 \times 10^{12}$  VP (equivalent to ~ $1.4 \times 10^{10}$  VP/kg), equivalent to the NOAEL dose in the animal studies. In the Phase I study in patients with advanced solid carcinoma, the starting dose was a single intratumoral injection of  $1 \times 10^{10}$  VP ( $1.4 \times 10^8$  VP/kg) per tumor. This was administered to an initial 3 cohorts (n = 3 each) and escalated to a maximum of  $5 \times 10^{12}$  VP/tumor. As DLT was not observed with single injections of the highest dose, a repeat dose ( $5 \times 1 \times 10^{12}$  VP), was administered. No DLTs were reported in this patient population with the dosing regimen described.

### 1.4 Patient Population

Patients with advanced, metastatic gastric and gastroesophageal junction adenocarcinoma that has received at least 2 lines of therapy for advanced/metastatic disease. Patients must be PD-L1 positive, as defined as CPS  $\geq$  1, and have measurable disease for the primary study endpoint of overall response rate by iRECIST.

# **2 OBJECTIVES**

### 2.1 Primary Objective

- To examine the efficacy of OBP-301 with pembrolizumab in PD-L1 positive advanced gastric and gastroesophageal junction adenocarcinoma in the 3rd or 4th line setting, as assessed by the iRECIST response rate.
- To examine the safety of multiple OBP-301 intratumoral injections in combination with pembrolizumab in advanced gastric and gastroesophageal junction adenocarcinoma.

### **Secondary Objectives**

The secondary objectives of the study are:

• To examine other measures of efficacy of the combination of OBP-301 with pembrolizumab in advanced gastric and gastroesophageal junction adenocarcinoma including the disease control rate, duration of response, overall survival and progression free survival.

### 2.2 Exploratory Objective

- To examine the tumor-immune microenvironment prior to and following OBP-301 and pembrolizumab therapy as assessed by bulk RNA sequencing and single-cell RNA sequencing.
- To examine and characterize the immune infiltrate by multi-parameter flow cytometry.

# **3 STUDY DESIGN**

### 3.1 Study Overview

This is a phase II study of OBP-301 with pembrolizumab in advanced gastric and GEJ adenocarcinoma that has progressed on at least 2 lines of prior therapy for advanced disease. This study will examine the addition of OBP-301 with pembrolizumab in this exact patient population.

**Figure 4.** Study Schema. Patients will be enrolled in the study in two stages. The first stage will be 18 patients. If 3 or more patients respond to the combination therapy, the study will move forward to stage 2, with 19 more patients enrolled. In the overall study population of 37 evaluable patients, 9 or more patients with an objective response would indicate a positive study.

The study schema is provided in **Fig 4.** Patients will be enrolled in a two stage design, with 18 patients in the first stage. If 3 or more patients respond to the combination therapy, the study will move forward to stage 2, with 19 more patients enrolled. Patients will receive  $1 \times 10^{12}$  VP/ tumor injection with Pembrolizumab (200 mg IV every 3 weeks). The tumor will be injected with OBP-301 four times (d1, d15, d29, d43). The preference is to inject the primary tumor endoscopically. Metastatic lesions may be injected on a case-by-case basis after discussion with the PI ([name]). All patients treated with OBP-301 will be eligible for the safety cohort.

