	
 
treatment, with the exception of prostate cancer controlled with androgen deprivation therapy.
 
7. Has received a live vaccine within 30 days of planned start of study therapy.
 
8. Patients known to have acute or chronic active hepatitis B virus (HBV), hepatitis C virus (HCV), or human immunodeficiency virus (HIV).
 
9. Has any evidence of active, non-infectious pneumonitis or interstitial lung disease requiring steroids.
 
10. Has an active infection requiring systemic therapy within 2 weeks of Day 1.
 
11. Has known psychiatric or substance abuse disorders that would interfere with cooperation with the requirements of the trial.
 
12. Is pregnant or breastfeeding, or expecting to conceive or father children within the projected duration of the trial, starting with the screening visit through 120 days after the last dose of trial treatment.
 
13. Previous severe hypersensitivity to another monoclonal antibody
 
14. Has a history or current evidence of any condition, therapy, or laboratory abnormality that might confound the results of the trial, interfere with the subject's participation for the full duration of the trial, or is not in the best interest of the subject to participate, in the opinion of the treating investigator.
 
15. Uncontrolled intercurrent illness including, but not limited to, uncontrolled diabetes, ongoing or active infection, symptomatic congestive heart failure, unstable angina pectoris, cardiac arrhythmia, or psychiatric illness/psychological incompetence, whereby in the opinion of the Investigator the patient is assessed as being unable to provide information, consent, or comply with the
 

	16. Patients who are pregnant or breastfeeding, or expecting to conceive or father children within the projected timeframe of the study, starting from the time of the Screening Visit through 4 months (120 days) after the last OBP-301 administration. Females of childbearing potential must have a negative serum or urine pregnancy test at Screening. A female not of childbearing potential is one who has undergone bilateral oophorectomy or who has had no menses for 12 consecutive months.
Study Procedures:	1. OBP-301 $2x10^{12}$ VP / tumor injection every 2 weeks x four injections.
	* Up to one additional injection may be considered in discussion with the PI ([name]).
	2. Pembrolizumab 200 mg intravenous every 3 weeks
Study Endpoints:	Primary Endpoint:

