### 5.2 Dosage and Treatment

1. OBP-301  $2x10^{12}$  viral particles/ tumor injection every 2 weeks x 4 injection encounters.

\* Up to 1 additional tumor injection encounter may be considered in discussion with the PI ([name]) which may be given 2 weeks after the 4th injection of OBP-301.

\* OBP-301 will be administered as a fixed dose to the tumor. The target dose of OBP-301 injection will be  $2x10^{12}$  VP (i.e. 1 vial), and a minimum of  $1x10^{12}$  VP (i.e. 1 ml). Specifically, inject as much OBP-301 as possible, but within 1 - 2 mL. The maximal injection volume of 2.0 mL is preferred (2  $x10^{12}$  VP per lesion) and should be injected as long as this is technically possible. At least 1 mL OBP-301 should be injected to the same location as the 1st and 2nd injection even though the primary tumor mass may have decreased and may be hard to locate.

\* OBP-301 will be administered to one lesion. If the gastroesophageal tumor is multifocal, only the largest lesion will be targeted.

\* For patients with tumors not assessable by endoscopy, injection via interventional radiology procedure is permitted, applying the same dosing principles above.

\* Note that it is expected that some amount of material will be used to prime the injection device (i.e. 0.8 mL for a Carre-Locke injection needle). This will be discarded as per standard procedure.

2. Pembrolizumab 200mg intravenous every 3 weeks until disease progression.

Page 35 V8.0

Please note that the Pharmacy manual, which is used for all OBP-301 studies globally, also indicates another OBP-301 dose administration option (plan B). This protocol will only use Plan A (i.e. fixed dose administration).

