### 5.2.2 Selection and Timing and IP Administration for each Patient

OBP-301 ( $2 \times 10^{12}$  VP/vial) is administered as intratumoral injection into a primary gastric or GEJ tumor mass that is suitable for injection, eg greater than 1 cm in size and in a location amenable for endoscopic injection. For patients with tumors not assessible by endoscopy, injection via interventional radiology procedure is permitted, applying the same dosing principles described herein. The largest diameter of the lesion will determine the volume of OBP-301 injected. The rationale for this is to ensure adequate penetration of the viral particals throughout the tumor.

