# 6.1.2 Treatment Phase

Pembrolizumab infusions will be administered every 3 weeks  $\pm$  3 days until disease progression or patient is withdrawn for another reason. OBP-301 is to be administered prior to pembrolizumab in this patient population. All patients will receive OBP-301 at 2 x10^12 viral particles/ tumor injection administered every two weeks x 4 injection encounters. The tumor will be injected with OBP-301 four times (day 1, day 15, day 29, day 43). However, there may be some exceptions for OBP-301 injections which are outlined below.

- A. Up to 1 additional tumor injection encounter may be considered in discussion with the PI ([name]), which may be given 2 weeks after the 4th injection of OBP-301.
- B. Patients who initially respond to combination therapy may be rechallenged with OBP-301 at the time of disease progression, after discussion with the principal investigator.

Criteria for the additional single dose of OBP-301 is that the patient has not had disease progression and has had no grade 3 or 4 events related to OBP-301.

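### The OBP-301 dose per injection is stated as 1×10^12 VP in one section and 2×10^12 VP in others, the animal NOAEL comparison is made only at the lower figure, and two volume rules conflict.

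*Combined protocol and SAP*

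**What the plan says.** **Dose per injection.** Section 3.1 gives 1×10^12 "VP/ tumor injection with Pembrolizumab (200 mg IV every 3 weeks") as what patients will receive, with no range, target or floor. The study procedures in the synopsis give 2×10^12 "VP / tumor injection every 2 weeks x four injections". Section 6.1.2 says: "All patients will receive OBP-301 at 2 x10 12 viral particles/ tumor injection administered every two weeks x 4 injection encounters". Section 5.2 also gives 2×10^12 VP, as a target equal to one vial, and adds a minimum of 1×10^12 VP (1 mL). The full 2 mL is preferred where technically possible.

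**Volume rule.** Section 5.2 states that "OBP-301 will be administered as a fixed dose to the tumor". It notes that the pharmacy manual contains another option and excludes it: "This protocol will only use Plan A (i.e. fixed dose administration"). Section 5.2.2 says: "The largest diameter of the lesion will determine the volume of OBP-301 injected". It gives no table or formula linking diameter to volume.

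**Animal comparison.** Sections 1.1.1.2 and 1.3 take a NOAEL of about 10^10 VP/kg, scale it to 70 kg for an HED of 7×10^11 VP, and describe 1×10^12 VP as equivalent to the NOAEL. Section 1.3 attaches that figure to this trial, "with the highest proposed clinical dose in this study". Section 1.1.1.2 says that the margin for systemic toxicity is adequate.

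**Phase I history.** Section 1.1.2 gives 1×10^12 VP/tumor as the top of the single-dose range in the first human study. Section 1.3 says that escalation in the phase I study reached 5×10^12 VP/tumor.

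**Priming.** Section 5.2 expects that "some amount of material will be used to prime the injection device (i.e. 0.8 mL for a Carre-Locke injection needle") and that this material is discarded.

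**The concern.** These are all current protocol sections, not a record of changes, and they cannot all be followed. An injection of 2×10^12 VP meets section 5.2 but is twice what section 3.1 says patients receive. A site reading 5.2.2 would look for a diameter rule that the protocol does not supply and that 5.2 appears to rule out.

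The dose of the investigational product is the basis of a primary objective, the safety of multiple injections (section 2.1). It also bears on the per-protocol population (section 8.4.4), which requires four doses given according to the protocol. If the protocol states two doses, adherence to it is not well defined.

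The animal comparison is part of the safety justification. An ethics committee or monitoring board reading 1.3 would conclude that the highest dose in this trial sits at about the NOAEL. The dosing sections schedule twice the dose for which that was said.

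**Working it through.** **Inputs**

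- NOAEL: about 10^10 VP/kg (sections 1.1.1.2 and 1.3)
- Body weight used by the plan: 70 kg (same sections)
- Product strength: 2 mL per vial at 1×10^12 VP/mL (section 5.1, Table 1)
- Doses: 1×10^12 VP (3.1, 1.3); 2×10^12 VP (synopsis, 5.2, 6.1.2)
- Priming loss: 0.8 mL for one named endoscopic needle (5.2)

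**Step 1. Reproduce the plan's figures.**

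HED = 10^10 × 70 = 7×10^11 VP, as stated.

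1×10^12 / 70 = 1.43×10^10 VP/kg, which agrees with the stated value of about 1.4×10^10.

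**Step 2. Apply the same formulas to both doses.**

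| Dose per injection | VP/kg at 70 kg | Ratio to HED | Four injections |
|---|---|---|---|
| 1×10^12 VP | 1.43×10^10 | 1×10^12 / 7×10^11 = 1.43 | 4×10^12 VP |
| 2×10^12 VP | 2.86×10^10 | 2×10^12 / 7×10^11 = 2.86 | 8×10^12 VP |

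Equivalence to the NOAEL is already loose at the lower dose, at 1.43 times the HED.

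**Step 3. Range over body weight.** The documents use 70 kg only, so 50 to 100 kg is an assumption. Ratio = dose / (weight × 10^10).

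- At 1×10^12 VP: 2.0 (50 kg) down to 1.0 (100 kg)
- At 2×10^12 VP: 4.0 (50 kg) down to 2.0 (100 kg)

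**Step 4. Place the higher dose among the other data in the documents.**

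- Animals: section 1.1.1.2 reports minor liver-cell damage at 10^11 VP/kg intramuscularly, and 10^11 / 2.86×10^10 = 3.5 times the higher clinical dose. It reports no deaths at about 10^12 VP/kg, which is 35 times that dose.
- Humans: section 1.1.2 (ongoing hepatocellular carcinoma study) reports a single dose of 3×10^12 VP in 3 subjects without dose-limiting toxicity.

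**Step 5. Volume rules side by side.** Section 5.2 sets a fixed dose, limited to 1 to 2 mL by what is technically possible. Section 5.2.2 sets volume by lesion diameter. The first makes volume depend on feasibility and the second on size, so they are different rules.

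**Step 6. Priming, conditional.** If the 0.8 mL comes out of the same 2 mL vial, 2.0 − 0.8 = 1.2 mL remains. At 1×10^12 VP/mL that is 1.2×10^12 VP. This is below the 2×10^12 VP target and above the 1×10^12 VP minimum.

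**The case against.** The strongest reply is that section 5.2 is the operative dosing section and is clear: a target, a minimum, a volume range and a named plan. Sections 3.1 and 1.3 and the diameter sentence in 5.2.2 would then be leftovers that no site would act on. Part of this stands. The diameter sentence has no table behind it and 5.2 expressly excludes the alternative plan, so it is weak evidence that dosing would actually diverge. But 3.1 is the study overview and 1.3 carries the safety argument. Nor can the figure in 3.1 be read as the 5.2 minimum, because it is given as what patients receive.

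A reader might infer several stronger points that the documents do not support.

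- **That the contradiction itself produces a two-fold spread of doses across sites.** Section 5.2 deliberately permits 1 to 2 mL, so a mixture of doses would remain after 3.1 was corrected.
- **That priming leaves patients 40% under target.** That holds only if priming comes from the same vial, which is not stated. The figure is for one needle, injection by interventional radiology is also allowed, and 1.2 mL is within the permitted range. Section 5.2.1.4 refers to a pharmacy brochure, not available here, for further preparation detail.
- **That the risk summary understates exposure.** Section 1.2 makes no NOAEL or HED claim. The multiple of 2.86 should be read beside the animal and human data in Step 4. Those data do not repair the comparison in 1.3, but they belong next to it.
- **That outcomes must be summarised by delivered dose.** This is a preference. With 37 evaluable patients and volume limited by feasibility, such a summary would be confounded with lesion characteristics.

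**Conclusion.** The contradiction is real and should be corrected. Two doses per injection, a factor of two apart, stand in current text. The NOAEL comparison is made only at the lower, although 1.3 calls that the highest in the study. At 70 kg the dose in the dosing sections is 2.86 times the HED, against 1.43 times for the dose that was compared. Across an assumed 50 to 100 kg the ratio at 2×10^12 VP runs from 4.0 to 2.0. The volume sentence in 5.2.2 conflicts with 5.2, and sections 1.1.2 and 1.3 disagree on the top phase I dose (1×10^12 against 5×10^12 VP/tumor). Section 1.3 also mentions a repeat dose of 5 × 1×10^12 VP. A reader might take the 5×10^12 VP to be that total, but the text gives it as a maximum per tumor reached before repeat dosing.

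The priming point is secondary and conditional. None of this touches the two-stage design: the boundaries (2 or fewer of 18; 9 or more of 37) take no dose input, and they give a type I error of 0.087 and power of 0.806, within the stated 10% and 80%. This conclusion takes no position on which dose or volume rule is correct, nor on whether the higher dose is safe.

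**What to change.** 1. The sponsor and investigator should reconcile the synopsis and sections 1.3, 3.1, 5.2, 5.2.2 and 6.1.2 to one dose statement, including any target and minimum, and one volume rule.
2. Reconcile sections 1.1.2 and 1.3 on the top phase I dose, making clear whether each figure is per injection or cumulative.
3. Recompute the HED/NOAEL comparison in 1.1.1.2 and 1.3 for the highest dose that the reconciled protocol allows, and revise the wording on equivalence and margin to match. Cite the human exposure above 1×10^12 VP from section 1.1.2 alongside it.
4. In 5.2, state whether the one-vial target is before or after the priming loss.

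The cost is one protocol amendment with the ethics committee submission required by section 9.2, and a line of arithmetic. The stated margin may look less favourable afterwards. Sample size, decision boundaries and analysis methods do not change.
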